8.3 Repeated or Unscheduled Assessments of Safety Parameters

If a subject has repeated assessments before the start of investigational product, then the results from the final assessment made prior to the start of investigational product during phase of interest will be used as baseline/Week 0. If end of phase assessments are repeated or unscheduled, the last post-baseline/Week 0 assessment will be used as the end of phase assessment for generating descriptive statistics. However, all post-baseline/Week 0 assessments will be used for PCI value determination and all assessments will be presented in the data listings.

8.4 Incomplete Date of Diagnosis

When computing the time since diagnosis, any missing days (of month) will be imputed as the 15th for diagnosis dates that precede screening. If imputed date is after screening, then screening date will be used as imputed diagnosis date.

8.5 Missing Date of Investigational Product

When the date of the last dose of investigational product is missing for a subject in the Safety Set for the acute or maintenance phases, all efforts should be made to obtain the date from the investigator. If it is still missing after all efforts, then the last visit date when investigational product was returned will be used in the calculation of treatment duration.

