5.6.2 Measurement of Treatment Compliance

Summaries of compliance will be produced for each of the three Safety Analysis Sets (Double-blind Acute Phase, Open-label Acute Phase and Double-blind Maintenance Phase).

Frequencies and percentages of subjects will be presented for the following categories: <80%, 80-120%, and >120%. Any treatment compliance calculations conducted at the site will be used for study management purposes. Therefore, those values will not be reconciled with values calculated during data analysis. Summary statistics (n, mean, SD, median, Q1, Q3, minimum, maximum) will also be presented.

Compliance is calculated for each phase and defined as:

$$\frac{\text{Overall Number of tablets dispensed} - \text{Overall Number of tablets returned}}{[\text{Date of Last Dose} - \text{Date of First Dose} + 1] \times \text{Number of Tablets Per Day}} \times 100 \%$$

The number of tablets per day is 4 for subjects in the weight groups of 18 to $\leq 23\text{kg}$, >23 to $\leq 35\text{kg}$, and >50 to $\leq 90\text{kg}$ regardless of treatment arm or phases. The number of tablets per day is 6 for subjects in the >35 to $\leq 50\text{kg}$ weight group regardless of treatment arm or phases.

Additionally, to examine subject-level compliance across study phases, these parameters will be listed by subject and phase.

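### The compliance formula counts unreturned tablets as taken; paired with the fallback last-dose date, it can file children of unknown intake as more than 120% compliant

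*SAP*

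**What the plan says.** SAP 5.6.2 defines compliance for each phase. The numerator is "Overall Number of tablets dispensed" minus "Overall Number of tablets returned". The denominator is the number of days from first dose to "Date of Last Dose", counted inclusively, times tablets per day (4 or 6 by weight group). Results are banded: "Frequencies and percentages of subjects will be presented for the following categories: <80%, 80-120%, and >120" (per cent). Summary statistics and a listing by subject and phase are also planned. The section gives no rule for packs that are never brought back, and it says that compliance figures worked out at the sites will not be reconciled with these.

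SAP 8.5 covers a missing date of last dose. First, "all efforts should be made to obtain the date from the investigator". If that fails, "then the last visit date when investigational product was returned will be used in the calculation of treatment duration". SAP 8.6.2, on medication stop dates, replaces the same missing date with the last visit date instead.

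The schedules of assessments have product both collected and dispensed at Weeks 2 and 4 of each acute phase and at Visit 5 (Weeks 2-4) and Week 13 of maintenance. Protocol 6.3.2 supplies double-blind product in one-week wallets. Protocol 6.5 has subjects bring unused product and empty packaging to every visit, for accounting by sealed container or by tablet.

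**The concern.** A child who stops attending returns nothing from the last dispensing, so the formula credits that whole supply as swallowed. If the last-dose date is also missing, the fallback sets it to the last visit at which product came back, which at an intermediate visit is the day that supply was issued. The numerator then holds a full interval of tablets for which the denominator has no days.

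The result is a specific wrong number. A child whose intake after that visit is unknown is placed in the over-compliant band and pulls the arm mean upward. Compliance is tabulated by arm in a study that compares two doses, so the table should not present unknown intake as excess intake, least of all if the arms differ in loss to follow-up.

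**Working it through.** The plan states no compliance figure for lost children, so there is none to reproduce. As a check on the formula, a fully adherent completer gives 56t/56t = 100% in an acute phase and 182t/182t = 100% in maintenance, where t is tablets per day (4 or 6).

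**Inputs from the documents.** Acute visits at Weeks 2, 4 and 8; maintenance Visit 5 once in Weeks 2-4, then Weeks 13 and 26; visit window ±3 days; the formula in SAP 5.6.2; the fallback in SAP 8.5.

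**Assumptions.** The documents do not give the quantity dispensed per visit; it is taken as just enough to reach the next scheduled visit (range: up to 7 days extra). Adherence a up to the last return visit is taken as 50-100%. The 8.5 date is used in 5.6.2.

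**Formula.** Let v be the day of the last return visit and n the day of the next scheduled visit. Tablets dispensed are n·t, and tablets returned at or before v are v·t·(1 − a). The denominator is v·t. So

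compliance = 100 × [n − v(1 − a)] / v = 100 × [a + (n − v)/v].

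Tablets per day cancel.

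| Last return visit | v | n | a = 100% | a = 80% | a = 50% |
|---|---|---|---|---|---|
| Acute Week 2 | 14 | 28 | 200% | 180% | 150% |
| Acute Week 4 | 28 | 56 | 200% | 180% | 150% |
| Maintenance Visit 5 at Week 2 | 14 | 91 | 650% | 630% | 600% |
| Maintenance Visit 5 at Week 3 | 21 | 91 | 433% | 413% | 383% |
| Maintenance Visit 5 at Week 4 | 28 | 91 | 325% | 305% | 275% |
| Maintenance Week 13 | 91 | 182 | 200% | 180% | 150% |

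**Threshold for the top band.** In the equal-interval rows (n − v)/v = 1, so the value exceeds 120% whenever a exceeds 20%. After Visit 5 it exceeds 120% at any prior adherence.

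**Sensitivity, starting from the 200% cases.**
- Visit 3 days early at Week 2: (11 + 14)/11 = 227%.
- Visit 3 days late at Week 2: (17 + 14)/17 = 182%, or (14 + 14)/17 = 165% if the first supply ran out on day 14.
- Seven days of extra supply: 35/14 = 250%, 63/28 = 225%, 189/91 = 208%.
- Open-label bottles (60 × 600 mg or 40 × 1200 mg), lost after Week 4, with the SAP's tablets per day: (112 + 120)/112 = 207% at 4 a day; (168 + 180)/168 = 207% at 6 a day.

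**Stop date known, last supply not returned, a = 100%.** Here SAP 8.5 plays no part.
- Acute stop at Week 5 after the Week 4 visit: 56/35 = 160%.
- Maintenance stop at Week 14 after the Week 13 visit: 182/98 = 186%.
- Acute stop at the end of Week 4 after a last visit at Week 2: 28/28 = 100%, so no overstatement.

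**No return visit at all.** There is no fallback date, so compliance is undefined.

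**The case against.** The strongest objection is that the pairing is inferred. SAP 8.5 limits its date to treatment duration, which SAP 5.6.1 reports as a separate item. If the date is not carried into 5.6.2, compliance is missing for these children and not inflated. That stands as a caveat. Against it, the 5.6.2 denominator is itself a first-to-last-dose duration, and the SAP offers no other date rule for compliance. Overstatement with a known stop date does not depend on 8.5.

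Second, the route is narrow. The fallback applies only after the investigator has been asked. Protocol 4.5 requires the stopping date and total amount taken to be recorded in source at discontinuation. Protocol 4.5.2 requires 3 contact attempts, one of them written and asking for unused product back. This stands: few children may be affected. The amount recorded in source does not correct the value, however, because the formula does not use it.

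Third, a reader can spot these cases. The top band is tabulated separately, the median, quartiles and maximum are shown, and listings by subject are planned. This also stands and limits the harm, but the band still mixes true over-use with unknown use.

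Fourth, counting only supply that was brought back introduces its own selection, and wallet-level returns may sit on the site accountability form and not in the database. Both are fair costs of the fix.

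**Conclusion.** The point holds as a correctable flaw in one derivation. Followed as written, SAP 5.6.2 treats supply of unknown fate as taken. With the 8.5 date in the denominator, a lost child scores about 150-200% after acute Week 2, acute Week 4 or maintenance Week 13 (somewhat more or less with early or late visits or spare supply), and about 275-650% after Visit 5. These sizes rest on the three assumptions listed with the calculation.

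A reader might infer more than the documents support:
- **That every lost child scores at least 200%.** In the equal-interval cases 200% is the value at perfect prior adherence, exact supply and on-time visits; it is not a floor. Only loss after Visit 5 exceeds 200% at any prior adherence.
- **That the worst adherers are being hidden.** Nothing in the documents says that lost children adhere worse; their intake is simply unknown.
- **That the arm means shift by a known amount.** The documents give no rate of loss, so no shift can be stated.
- **That the dose comparison is biased.** Efficacy uses the phase Safety Analysis Sets, and no primary, secondary or sensitivity analysis described in the SAP uses compliance. The effect is confined to the descriptive compliance summaries.

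This is a minor point, worth making because it is cheap to correct.

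**What to change.** In SAP 5.6.2, treat supply for which no packaging came back (full, part-used or empty) as unknown. Compute compliance only over dispensing intervals with accounted-for packs, or set it to missing. State whether the 8.5 date feeds 5.6.2, and do not pair it with tablets dispensed on that date. Report by arm and phase the number of children with unreturned supply. Reconcile the 8.5 fallback with the different one in 8.6.2.

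Leaving out the unreturned last dispensing returns 100 × a in every scenario: 100% at full prior adherence, 80% at 80%. Extending the denominator to the end of the dispensed supply is weaker, because it still credits tablets of unknown fate: at 80% prior adherence it gives (0.8v + n − v)/n, which is 90% in the equal-interval cases and 94-97% after Visit 5.

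The cost is SAP wording and one derivation, provided that returns can be linked to dispensings in the database, which the documents do not confirm. One-week wallets and container- or tablet-level accounting make this feasible in principle. The downside is that compliance is missing or partial for a few children and describes only supply that was brought back.

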8.6 Missing Date Information for Prior or Concomitant Medications

For prior or concomitant medications, incomplete (i.e., partially missing) start date and/or stop date will be imputed. When the start date and the stop date are both incomplete for a subject, the start date will be imputed first.

8.6.1 Incomplete Start Date

The following rules will be applied to impute the missing numerical fields. If the stop date is complete and the imputed start date is after the stop date, then the start date will be imputed using the stop date.

Missing day and month

- If the year of the incomplete start date is the same as the year of the date of the first dose of investigational product, then the day and month of the date of the first dose of investigational product will be assigned to the missing fields.
- If the year of the incomplete start date is before the year of the date of the first dose of investigational product, then December 31 will be assigned to the missing fields.
- If the year of the incomplete start date is after the year of the date of the first dose of investigational product, then 01 January will be assigned to the missing fields.

Missing month only

- The day will be treated as missing and both month and day will be replaced according to the above procedure.

Missing day only

- If the month and year of the incomplete start date are the same as the month and year of the date of the first dose of investigational product, then the day of the date of the first dose of investigational product will be assigned to the missing day.
- If either the year is before the year of the date of the first dose of investigational product or if both years are the same but the month is before the month of the date of the first dose of investigational product, then the last day of the month will be assigned to the missing day.
- If either the year is after the year of the date of the first dose of investigational product or if both years are the same but the month is after the month of the date of the first dose of investigational product, then the first day of the month will be assigned to the missing day.

8.6.2 Incomplete Stop Date

The following rules will be applied to impute the missing numerical fields. If the date of the last dose of investigational product is missing, then the last visit date will be imputed. If the imputed stop date is before the start date (imputed or non-imputed start date), then the imputed stop date will be equal to the start date.

Missing day and month

- If the year of the incomplete stop date is the same as the year of the date of the last dose of investigational product, then the day and month of the date of the last dose of investigational product will be assigned to the missing fields.
- If the year of the incomplete stop date is before the year of the date of the last dose of investigational product, then 31 December will be assigned to the missing fields.
- If the year of the incomplete stop date is after the year of the date of the last dose of investigational product, then 01 January will be assigned to the missing fields.

Missing month only

- The day will be treated as missing and both month and day will be replaced according to the above procedure.

Missing day only

- If the month and year of the incomplete stop date are the same as the month and year of the date of the last dose of investigational product, then the day of the date of the last dose of investigational product will be assigned to the missing day.

- If either the year is before the year of the date of the last dose of investigational product or if both years are the same but the month is before the month of the date of the last dose of investigational product, then the last day of the month will be assigned to the missing day.
- If either the year is after the year of the last dose of investigational product or if both years are the same but the month is after the month of the date of the last dose of investigational product, then the first day of the month will be assigned to the missing day.

8.7 Missing Date Information for Adverse Events

For AEs, only incomplete (i.e., partially missing) start dates will be imputed, to determine if the event is treatment emergent.

8.7.1 Incomplete Start Date

Follow same rules as in Section [8.6.1](#).

8.7.2 Incomplete Stop Date

Not applicable as duration of AEs is not presented.

8.8 Missing Severity Assessment for Adverse Events

If severity is missing for an AE starting prior to the date of the first dose of investigational product, then a severity of “Mild” will be assigned. If the severity is missing for a TEAE starting on or after the date of the first dose of investigational product, then a severity of “Severe” will be assigned. The imputed values for severity assessment will be used for incidence summaries, while the actual values will be used in data listings.

8.9 Missing Relationship to Investigational Product for Adverse Events

If the relationship to investigational product is missing for a TEAE starting on or after the date of the first dose of investigational product, a causality of “Related” will be assigned. The imputed values for relationship to double-blind investigational product will be used for incidence summaries, while the actual values will be presented in data listings.

8.10 Character Values of Clinical Laboratory Variables

If the reported value of a clinical laboratory variable cannot be used in a statistical analysis (e.g., if a character string is reported for a numerical variable), then the appropriately determined coded value will be used in the statistical analysis. However, the actual values as reported in the database will be presented in data listings.

Table 4: Examples for Coding of Special Character Values for Clinical Laboratory Variables

Clinical Laboratory Test	Possible Results (in SI units)	Coded Value for Analysis
Chemistry: ALT	<5	0
Chemistry: AST	<5	0
Chemistry: Total Bilirubin	<2	0
Urinalysis: Glucose	≥55	Positive
	≤0	Negative
Urinalysis: pH	≥8.0	8.0
[REDACTED]	[REDACTED]	[REDACTED]

11. SCHEDULE OF EVENTS

Table 5: Double-blind Acute Phase

Visit	1 (Screening)	Recommended Telephone call ^a	2 (Baseline)	3 ^b	3.1	3.2 ^{c, d, e, f}	6 ^g
Week/Month ^h	Day -21 to -3	Day -7 to -4	Week 0	Week 2	Week 4	Week 8/Withdrawal	Follow-up
Informed consent	✓						
Inclusion/exclusion criteria	✓		✓				
Demographics	✓						
Medical and medication history	✓						
Physical examination	✓					✓	
Height	✓					✓	
Weight	✓		✓			✓	
Vital signs	✓		✓	✓	✓	✓	
Biochemistry (includes C-reactive protein) and hematology	✓					✓	
Pregnancy test (for females of childbearing potential only) ⁱ	✓		✓	✓	✓	✓	
Pharmacokinetic blood sampling (at participating sites only)						✓	
[REDACTED]			✓				
Urinalysis	✓					✓ ^j	
[REDACTED]	✓						
Stool sample (culture) ^{k, l}	✓						
[REDACTED]	✓					✓	

Table 5: Double-blind Acute Phase

Visit	1 (Screening)	Recommended Telephone call ^a	2 (Baseline)	3 ^b	3.1	3.2 ^{c, d, e, f}	6 ^g
Week/Month ^h	Day -21 to -3	Day -7 to -4	Week 0	Week 2	Week 4	Week 8/Withdrawal	Follow-up
Review DUCS instructions, ability to read and understand e-diary with subject/caregiver	✓						
Subject/caregiver e-diary entry: rectal bleeding, stool frequency, DUCS, and Overall Current Health ^m	✓		✓	✓	✓	✓	
Assessment of e-diary compliance ^a		✓					
Global Change in Health ^l				✓	✓	✓	
IMPACT III ⁿ			✓			✓	
PUCAI (where applicable)			✓			✓	
Average stool frequency ^{o, p, q}			✓	✓	✓	✓	
Average rectal bleeding ^{o, p, q}			✓	✓	✓	✓	
PGA ^{p, q}			✓	✓	✓	✓	
Endoscopy (flexible sigmoidoscopy or colonoscopy) for study eligibility ^{h, q, r}	✓		✓				
Endoscopy (flexible sigmoidoscopy or colonoscopy), where possible for subjects who are not entering into the Open-label Acute Phase) ^q						✓	
Calculate partial UC-DAI			✓			✓	
IRT entry	✓		✓	✓	✓	✓	
Investigational product dispensed			✓	✓	✓	✓ ^s	

Table 5: Double-blind Acute Phase

Visit	1 (Screening)	Recommended Telephone call ^a	2 (Baseline)	3 ^b	3.1	3.2 ^{c, d, e, f}	6 ^g
Week/Month ^h	Day -21 to -3	Day -7 to -4	Week 0	Week 2	Week 4	Week 8/Withdrawal	Follow-up
Investigational product collected and compliance calculated				✓	✓	✓	
Adverse events	✓	✓	✓	✓	✓	✓	✓
Concomitant medication	✓		✓	✓	✓	✓	✓
Re-randomization (subjects entering Double-blind Maintenance Phase only)						✓	

Abbreviations: DUCS=Daily Ulcerative Colitis Scale for children and caregivers; eCRF=electronic case report form; e-diary=electronic diary; IRT= interactive response technology; PGA=Physician's Global Assessment; PUCAI=Pediatric Ulcerative Colitis Activity Index; UC-DAI=Ulcerative Colitis Disease Activity Index.

^a Approximately 4 to 7 days prior to the Baseline Visit (Visit 2) and prior to each subsequent visit (Visits 3, 3.1, and 3.2), it is recommended that site staff telephone the subject or the subject's caregiver to remind them to enter UC-DAI symptoms (rectal bleeding and stool frequency) into the e-diary every night, even if the subject has no symptoms.

^b Subjects may enter into the Open-label Acute Phase beginning at Visit 3 (after a minimum of 2 weeks double-blind treatment) and at any time until the end of the Double-blind Acute Phase provided all criteria have been met.

^c Subjects will continue into the Open-label Acute Phase if they have not met the criteria to enter the Double-blind Maintenance Phase and are eligible to continue into the Open-label Acute Phase.

^d Subjects will continue into the Double-blind Maintenance Phase if partial UC-DAI ≤ 1 (with rectal bleeding=0 and stool frequency ≤ 1 and PGA=0) and with mucosal healing (endoscopy score)=0 or 1, and are eligible to continue into the Double-blind Maintenance Phase.

^e This will be the final visit for subjects not entering the Open-label Acute Phase or the Double-blind Maintenance Phase.

^f The Baseline Visit (Visit 2) does not need to be repeated for subjects entering the Double-blind Maintenance Phase at the end of the Double-blind Acute Phase. Visit 3.2 will be considered the Week 0 visit for the next phase into which subjects are continuing.

^g Follow-up assessment in this phase applies only to subjects who are discontinuing the study; may be performed via telephone call within 7 days of the last dose of investigational product.

^h A visit window of ± 3 days is permitted for all study visits except for the Screening Visit (Visit 1) and the Baseline Visit (Visit 2), which must occur 3 to 21 days following the Screening Visit (Visit 1). If the initial endoscopy is not adequate for mucosal healing score assignment due to inadequate bowel preparation, to allow for a repeat endoscopy to be conducted, the period of the Screening Visit (Visit 1) can be extended by an additional 14 days from the date of the initial endoscopy.

ⁱ The serum pregnancy test will be performed for all female subjects of childbearing potential at the screening visit (Visit 1) and Week 8/Withdrawal (Visit 3.2). Urine pregnancy tests will be performed at all other visits.

^j Urinalysis performed at this visit only for subjects who are not continuing into the Open-label Acute Phase.

¹ Stool samples collected for culture may be processed by local laboratories; however, results from the central laboratory analysis will prevail and will be entered in the eCRF.

^m Rectal bleeding, stool frequency, DUCS, and Overall Current Health e-diary entry is completed once a day before bedtime every day from the evening of the Screening Visit

Table 5: Double-blind Acute Phase

Visit	1 (Screening)	Recommended Telephone call ^a	2 (Baseline)	3 ^b	3.1	3.2 ^{c, d, e, f}	6 ^g
Week/Month ^h	Day -21 to -3	Day -7 to -4	Week 0	Week 2	Week 4	Week 8/Withdrawal	Follow-up

(Visit 1), preferably for at least the 3 days immediately prior to the Baseline Visit (Visit 2). Rectal bleeding, stool frequency, DUCS and Overall Current Health e-diary entry is completed once a day before bedtime for the 5 days immediately prior to Visits 3, 3.1, and 3.2 of the Double-blind Acute Phase.

^a Global Change in Health to be completed by caregivers of children aged 5-10 years and by children aged 11-17 years; IMPACT III to be completed by children aged 8-17 years only (see Section 4.3).

^b The average stool frequency and rectal bleeding scores will be calculated and available to the investigator through a report from the e-diary provider.

^c Components of the partial UC-DAI.

^d Components of the modified full UC-DAI.

^e For subjects entering the Double-Blind Acute Phase only: Subjects with an unconfirmed diagnosis of UC must have endoscopy performed during the Screening Visit (Visit 1).

Subjects with a previously confirmed diagnosis must have endoscopy at the Screening Visit (Visit 1) or at the Baseline Visit (Visit 2) if endoscopy has not been performed within 21 days prior to the Screening Visit (Visit 1).

^g Only for subjects continuing into the Open- label Acute or Double- blind Maintenance Phase.

Table 6: Open-label Acute Phase

Visit	Recommended Telephone call ^a	4	4.1	4.2 ^{b, c, d, e}	6 ^f
Week ^g	Day -7 to -4	Week 2	Week 4	Week 8/Withdrawal	Follow-up
Physical examination				✓	
Height				✓	
Weight				✓	
Vital signs		✓	✓	✓	
Biochemistry (includes C-reactive protein) and hematology				✓	
Pregnancy test (for females of childbearing potential only) ^h		✓	✓	✓	
Pharmacokinetic blood sampling (at participating sites only)				✓	
Urinalysis				✓	
██████████				✓	
Subject e-diary entry: rectal bleeding, stool frequency, DUCS, and Overall Current Health ⁱ		✓	✓	✓	
Assessment of e-diary compliance ^a	✓				
PUCAI (where applicable)				✓	
Average stool frequency ^{j,k,1}		✓	✓	✓	
Average rectal bleeding ^{j,k,1}		✓	✓	✓	
PGA ^{k,1}				✓	
Endoscopy (flexible sigmoidoscopy or colonoscopy), where possible ^k				✓	
IRT entry		✓	✓	✓	
Calculate partial UC-DAI				✓	

Table 6: Open-label Acute Phase

Visit	Recommended Telephone call ^a	4	4.1	4.2 ^{b, c, d, e}	6 ^f
Week ^g	Day -7 to -4	Week 2	Week 4	Week 8/Withdrawal	Follow-up
Investigational product dispensed		✓	✓	✓ ^m	
Investigational product collected and compliance calculated		✓	✓	✓	
Adverse events	✓	✓	✓	✓	✓
Concomitant medication		✓	✓	✓	✓
Re-randomization (subjects entering Double-blind Maintenance Phase only)				✓	

Abbreviations: DUCS=Daily Ulcerative Colitis Scale for children and caregivers; e-diary=electronic diary; IRT= interactive response technology; PGA=Physician's Global Assessment; PUCAI=Pediatric Ulcerative Colitis Activity Index; UC-DAI=Ulcerative Colitis Disease Activity Index.

^a Approximately 4 to 7 days prior to Visit 4 and prior to each subsequent visit (Visits 4.1 and 4.2), it is recommended that site staff telephone the subject or the subject's caregiver to remind them to enter UC-DAI symptoms (rectal bleeding and stool frequency) into the e-diary every night, even if the subject has no symptoms.

^b Subjects will continue into the Double-blind Maintenance Phase if partial UC-DAI ≤ 1 (with rectal bleeding=0 and stool frequency ≤ 1 and PGA=0) and are eligible to continue into the Double-blind Maintenance Phase.

^c Subjects will be withdrawn from the study if they have not achieved a partial UC-DAI ≤ 1 (with rectal bleeding=0 and stool frequency ≤ 1 and PGA=0).

^d This will be the final visit for subjects not continuing into the Double-blind Maintenance Phase.

^e The Baseline Visit (Visit 2) does not need to be repeated for subjects entering the Double-blind Maintenance Phase at the end of the Open-label Acute Phase. Visit 4.2 will be considered the Week 0 visit for the Double-blind Maintenance Phase.

^f Follow-up assessment in this phase applies only to subjects who are discontinuing the study; may be performed via telephone call within 7 days of the last dose of investigational product.

^g A visit window of ± 3 days is permitted for all study visits.

^h The serum pregnancy test will be performed for all female subjects of childbearing potential at Week 8/Withdrawal (Visit 4.2). Urine pregnancy tests will be performed at all other visits.

ⁱ Rectal bleeding, stool frequency, DUCS, and Overall Current Health e-diary entry is completed once a day before bedtime every day for 5 days immediately prior to Visits 4, 4.1 and 4.2 of the Open-label Acute Phase.

^j The average stool frequency and rectal bleeding scores will be calculated and available to the investigator through a report from the e-diary provider.

^k Components of the partial UC-DAI.

^l Components of the modified full UC-DAI.

^m Only for subjects continuing into the Double-blind Maintenance Phase.

Table 7: Double-blind Maintenance Phase

Visit	1 (Screening) ^a	Recommended Telephone call ^b	2 (Baseline) ^a	5	5.1	5.2	6 ^c
Day/Month ^d	Day -21 to -3	Day -7 to -4	Week 0	Weeks 2-4	Week 13	Week 26/ Withdrawal	Follow-up
Informed consent	✓						
Inclusion/exclusion criteria	✓		✓				
Demographics	✓						
Medical and medication history	✓						
Physical examination	✓				✓	✓	
Height	✓					✓	
Weight	✓		✓			✓	
Vital signs	✓		✓		✓	✓	
Biochemistry (includes C-reactive protein) and hematology	✓					✓	
Pregnancy test (for females of childbearing potential only) ^e	✓		✓	✓	✓	✓	
Pharmacokinetic blood sampling (at participating sites only)						✓	
Urinalysis	✓					✓	
[REDACTED]			✓				
[REDACTED]	✓						
Stool sample (culture) ^{f,g}	✓						
[REDACTED]	✓					✓	
Review DUCS instructions, ability to read and understand e-diary with subject/caregiver	✓						
Subject/caregiver e-diary entry: rectal bleeding, stool frequency, DUCS, and Overall Current Health ^h	✓		✓		✓	✓	
Assessment of e-diary compliance ^a		✓					

Table 7: Double-blind Maintenance Phase

Visit	1 (Screening) ^a	Recommended Telephone call ^b	2 (Baseline) ^a	5	5.1	5.2	6 ^c
Day/Month ^d	Day -21 to -3	Day -7 to -4	Week 0	Weeks 2-4	Week 13	Week 26/ Withdrawal	Follow-up
Global Change in Health ⁱ						✓	
IMPACT III ⁱ			✓			✓	
PUCAI (where applicable)			✓			✓	
Average stool frequency ^{j, k, l}			✓		✓	✓	
Average rectal bleeding ^{j, k, l}			✓		✓	✓	
PGA ^{k, l}			✓			✓	
Endoscopy (flexible sigmoidoscopy or colonoscopy) for study eligibility ^{d, l, m}	✓		✓				
Endoscopy (flexible sigmoidoscopy or colonoscopy), where possible ^l						✓	
IRT entry	✓		✓	✓	✓	✓	
Calculate partial UC-DAI			✓			✓	
Investigational product dispensed			✓	✓	✓		
Investigational product collected and compliance calculated				✓	✓	✓	
Adverse events	✓	✓	✓	✓	✓	✓	✓
Concomitant medication	✓		✓		✓	✓	✓

Abbreviations: DUCS=Daily Ulcerative Colitis Scale for children and caregivers; eCRF=electronic case report form; e-diary=electronic diary; IRT= interactive response technology; PGA=Physician's Global Assessment; PUCAI=Pediatric Ulcerative Colitis Activity Index; UC-DAI=Ulcerative Colitis Disease Activity Index.

^a The Screening Visit (Visit 1) and the Baseline Visit (Visit 2) in Table 7 apply only to subjects entering directly into the Double-blind Maintenance Phase.

^b Approximately 4 to 7 days prior to the Baseline Visit (Visit 2) and prior to each subsequent visit (Visits 5, 5.1, and 5.2), it is recommended that site staff telephone the subject or the subject's caregiver to remind them to enter UC-DAI symptoms (rectal bleeding and stool frequency) into the e-diary every night, even if the subject has no symptoms.

^c Follow-up assessment may be performed via telephone call within 7 days of the last dose of investigational product.

^d A visit window of ± 3 days is permitted for all study visits except for the Screening Visit (Visit 1) (must be 3 to 21 days) and the Baseline Visit (Visit 2), which must occur 3 to 21 days following the Screening Visit (Visit 1). If the initial endoscopy is not adequate for mucosal healing score assignment due to inadequate bowel preparation, to allow for a repeat endoscopy to be conducted, the period of the Screening Visit (Visit 1) can be extended by an additional 14 days from the date of the initial endoscopy.

^e The serum pregnancy test will be performed for all female subjects of childbearing potential at the screening visit (Visit 1) and Week 26/Withdrawal (Visit 5.2). Urine pregnancy tests will be performed at all other visits.

Table 7: Double-blind Maintenance Phase

Visit	1 (Screening) ^a	Recommended Telephone call ^b	2 (Baseline) ^a	5	5.1	5.2	6 ^c
Day/Month ^d	Day -21 to -3	Day -7 to -4	Week 0	Weeks 2-4	Week 13	Week 26/ Withdrawal	Follow-up

^g Stool samples collected for culture may be processed by local laboratories in addition to the assessment by the central laboratory. Central laboratory results will prevail and, as such, they will be the data entered into the eCRF.

^h Rectal bleeding, stool frequency, DUCS and Overall Current Health e-diary entry is completed once a day before bedtime every day during the Screening Visit (Visit 1), preferably for at least the 3 days immediately prior to the Baseline Visit (Visit 2). Rectal bleeding, stool frequency, DUCS and Overall Current Health e-diary entry is completed once a day before bedtime for the 5 days immediately prior to Visit 5.1 and Visit 5.2.

ⁱ Global Change in Health to be completed by caregivers of children aged 5-10 years and by children aged 11-17 years; IMPACT III to be completed by children aged 8-17 years only.

^j The average stool frequency and rectal bleeding scores will be calculated and available to the investigator through a report from the e-diary provider.

^k Components of the partial UC-DAI.

^l Components of the modified full UC-DAI.

^m For subjects entering the Double-blind Maintenance Phase directly: Subjects with a previously confirmed diagnosis must have endoscopy at the Screening Visit (Visit 1) or at the Baseline Visit (Visit 2). If the initial endoscopy is not adequate for mucosal healing score assignment due to inadequate bowel preparation, to allow for a repeat endoscopy to be conducted, the period of the Screening Visit (Visit 1) can be extended by an additional 14 days from the date of the initial endoscopy.
